4.4 Study Subjects

4.4.1 Disposition of Subjects

A clear accounting of the disposition of all subjects who enter the study will be provided, from screening to study completion.

Disposition information will be summarized for the All Treated analysis set for Part 1 and the ITT analysis set for Part 2 at the end of treatment and at the end of study, respectively. Subject enrollment will be summarized by country and investigator.

Descriptive statistics (mean, SD, median, and range) will be provided for time (in weeks) on study treatment as well as length of follow-up (in months). Time on treatment is defined as the interval between the first dose date and the last dose date or death date (censored) if die before End of Treatment visit. Time on study is defined the same way as OS with reversed censoring, i.e., a subject who died will be censored. Based on this definition, time on study is the same as length of follow up. The Kaplan-Meier method will be used to estimate the median time on treatment and on study.

4.4.2 Protocol Deviations

Major protocol deviations are defined as those deviations from the protocol that are likely to have an impact on subject's right, safety, well-being, and/or the validity of data for analysis. Major protocol deviations and any action to be taken regarding the exclusion of subjects or affected data from specific analyses are defined in the project-specific Protocol Deviation Specification.

Subjects with major protocol deviations will be listed. For Part 1, major protocol deviations will be based on clinical review mainly of the following categories: (1) Entered but did not satisfy eligibility criteria; (2) Developed withdrawal criteria but not withdrawn; (3) Received a disallowed concomitant treatment; (4) Received wrong treatment or incorrect dose; and (5) other. For Part 2, major protocol deviations will be summarized and presented by the classifications in Protocol Deviation Specification.

The number of subjects with major deviations from the protocol will be counted and documented together with their corresponding population type (Part 1) or treatment group (Part 2), and the reason/circumstances leading to the deviation. A summary of the number and percentage of enrolled subjects with a major protocol deviation by population type (Part 1) or randomized

subjects with a major protocol deviation by treatment group (Part 2) and overall, and by type of deviation will be provided.

4.5 Analysis Sets

The analysis sets for Part 1 and Part 2 will be defined separately. And the results for Part 1 and for Part 2 will also be summarized and presented separately. In Part 2, the stratification factors (prior RBC transfusion burden and IPSS risk group) used at the randomization, i.e., values entered into the IWRS, will be used for testing of the primary endpoint and the key secondary endpoints.

Upon database release, protocol deviation and analysis set outputs will be produced and will be sent to the sponsor for review. An analysis set classification meeting for Part 2 will be arranged to discuss the outputs and to decide which subjects and/or subject data will be excluded from certain analyses. Decisions made regarding the exclusion of subjects and/or subject data from analyses will be made prior to unblinding of Part 2 and will be documented and approved by the Sponsor.

A by-subject listing of analysis set details will be provided. This listing should include center, subject identifier, and inclusion/exclusion flag for each set and reason for exclusion from each set. All subjects screened should appear on this listing.

4.5.1 Efficacy Analysis Sets

Part 1 (Phase 2):

All Treated analysis set: includes all subjects who receive at least one dose of study drug. This analysis set will be used for all analyses of efficacy endpoints (except time to the 8 or 24-week RBC TI and duration of RBC TI), analyses of disposition, demographics, and baseline disease characteristics.

All Treated 8-week (24-week) TI responder analysis set: includes all treated subjects who do not have any RBC transfusion during any consecutive 8 (24) weeks starting from Study Day 1 until subsequent anti-cancer therapy if any, with the TI starting date between Study Day 1 and date of last dose of study medication + 30 days or End of Treatment Visit whichever occurs first. This analysis set will be used for analyses for time to RBC TI and duration of RBC TI.

Part 2 (Phase 3):

Intent-to-Treat (ITT) analysis set: includes all subjects randomized into the main study. This analysis set will be used for all analyses of efficacy and patient-reported outcomes (PRO) endpoints (except time to the 8 or 24-week RBC TI and duration of RBC TI), analyses of disposition, demographic, and baseline disease characteristics. Subjects will be classified according to assigned treatment group, regardless of the actual treatment received.

ITT 8-week (24-week) TI responder analysis set: includes all subjects in the ITT analysis set who do not have any RBC transfusion during any consecutive 8 (24) weeks starting from Study Day 1 until subsequent anti-cancer therapy if any, with the TI starting date between Study Day 1 and date of last dose of study medication + 30 days or End of Treatment Visit whichever occurs first. This analysis set will be used for analyses for time to the RBC TI and duration of RBC TI.

Modified ITT (MITT) analysis set: includes all ITT subjects who received at least one dose of study drug according to assigned treatment group. This analysis set will be used for sensitivity analyses for 8-week and 24-week RBC TI in the case there are subjects who were dosed, but didn't receive the assigned treatment.

Per-protocol (PP) analysis set: This analysis set is a subset of the ITT analysis set. Subjects with key protocol deviations will be excluded from the PP analysis set. The categories and terms of the key protocol deviations leading to exclusion are defined in the project-specific Protocol Deviation Specification.

Subjects in this analysis set will be analyzed according to the treatment to which they are randomized. This analysis set will be used for sensitivity analysis for 8-week and 24-week RBC TI.

4.5.2 Safety Analysis Sets

For both Part 1 and 2, the Safety analysis set includes all subjects who receive at least one dose of study drug. This analysis set will be used for all safety analyses and analyses of exposure. All subjects will be analyzed according to the treatment which they actually received.

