- a Posttreatment Follow-up Phase which will continue until death, loss to follow-up, withdrawal of consent, or the end of the study (whichever occurs first). The end of the main study is defined as 24 months after the randomization of the last subject in the main study of Part 2.
- An Extension Phase will begin after the end of the main study (24 months after the last subject was randomized in the main study of Part 2) and continue until subjects who entered from Part 2 of the main study participate in the study for at least 5 years from the first dose of imetelstat (including treatment and follow-up), or 3 years of post-treatment follow-up from the last dose of study treatment, whichever occurs later, or until death, withdrawal of consent, study termination, or until a subject is lost to follow-up.

In Part 2, approximately 45 evaluable subjects (in addition to the approximately 170 subjects who will be enrolled in the main study) will be enrolled in a separate Ventricular Repolarization (QTc) substudy investigating the effects of imetelstat exposure on ventricular repolarization. Subjects who are not evaluable for the QTc substudy primary electrocardiograms (ECG) endpoint may be replaced with new subjects. Serial ECGs will be obtained with PK samples on Day 1 of Cycle 1 as indicated in Attachment 11. The cardiac safety analysis in regard to ECG and concentration QTc analysis in the substudy based on the additional 45 subjects will be performed separately from the primary analysis of 170 subjects in the main study (refer to Attachment 11 for further details). Subjects who have enrolled into the Ventricular Repolarization substudy of Part 2 prior to Protocol Amendment 7 will continue with the assessments as required for the main study.

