In the main study of Part 2, approximately 170 subjects will be randomized in a 2:1 ratio to receive either imetelstat or placebo. Using a 2:1 ratio randomization and a 2-group continuity corrected Chi-square test with 0.05 (2-sided) significance level, 150 subjects are needed to achieve a power of approximately 88% to detect the difference between a RBC TI rate of 30% in the imetelstat group and a RBC TI rate of 7.5% in the placebo group. After correction for a 10% drop-out rate, a total of approximately 170 subjects (115 subjects in the imetelstat group and 55 subjects in the placebo group) will be needed. The overall study power from Part 1 and Part 2 is approximately 85%.

Efficacy data in Part 1 will be descriptively summarized based on the treated population. The proportion of subjects with 8-week RBC TI, 24-week RBC TI, CR, PR, mCR, hematologic improvement, and other binary endpoints will be summarized with percentage along with its 95% 2-sided exact confidence interval. Efficacy data in the main study of Part 2 will be compared between the imetelstat group and the placebo group based on the intent to treat population. Transfusion independence rates will be summarized with frequency and percentage along with a 2-sided 95% confidence interval for each treatment group. The comparison will be based on stratified Cochran-Mantel-Haenszel test adjusting for the stratification factors at a two-sided significance level of 0.05.

Safety variables are to be tabulated by descriptive statistics.

The ECG and concentration-QTc in the Ventricular Repolarization substudy as well as safety and limited efficacy based on the additional 45 evaluable subjects enrolled, will be performed separately from the primary analysis of 170 subjects in the main study of Part 2 (see Attachment 11). These data may only be available after the primary analysis of the main study of Part 2 has already been completed.

TIME AND EVENTS SCHEDULES

Table 1: Time and Events Schedule for Part 1 (Open-label, Imetelstat Treatment)

Study Procedures	Comments	PHASE	Treatment Phase (4-week cycles \pm 3 days)					Posttreatment Follow-up Phase
		Screening Phase	Cycle 1 Day 1 (predose)	Cycle 1 Day 8, 15, 22	Cycle 2 Day 1, 8, 15, 22	Cycle 3 until EOT Day 1	EOT Visit within 30 days after last dose	Survival Follow-up Every 12-16 weeks
Screening								
Informed consent		X						
Inclusion/exclusion criteria		X						
Medical history and demographics		X						
Study Medication Administration								

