4.5.5 Ventricular Repolarization Substudy Analysis Sets

The Ventricular Repolarization substudy analysis set includes all subjects who participated in Ventricular Repolarization substudy and received at least one dose of study drug.

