4.10 Safety Evaluation

All safety summaries and analyses will be based upon the Safety Analysis Set as defined in Section 4.5.2. Safety variables are to be tabulated by descriptive statistics (n, mean, median, standard deviation, minimum, and maximum; or n and percent). Missing safety data will generally not be imputed. As an exception, adverse events that have missing causality (after data querying) will be assumed to be related to study drug.

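### SAP 4.5.2 does not limit the Part 2 Safety set to the main study, so read literally it takes in dosed QTc-substudy subjects whom the protocol analyses separately

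*SAP*

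**What the plan says.** - SAP 4.5.1, ITT set for Part 2: "includes all subjects randomized into the main study".
- SAP 4.5.2, Safety set: "For both Part 1 and 2, the Safety analysis set includes all subjects who receive at least one dose of study drug". Subjects are analysed by the treatment they actually received.
- SAP 4.10: "All safety summaries and analyses will be based upon the Safety Analysis Set as defined in Section 4.5.2". SAP 4.8 puts the exposure summaries on the same set.
- SAP 4.5 keeps the two parts of the study apart: "And the results for Part 1 and for Part 2 will also be summarized and presented separately". It does not divide Part 2 into main study and substudy.
- SAP 4.5.5, substudy set: "includes all subjects who participated in Ventricular Repolarization substudy and received at least one dose of study drug".
- SAP 4.11.3 separates the ECG and exposure-response work from the main analysis. For other substudy safety data it refers back to the main-study SAP.
- Protocol Synopsis, Statistical Methods, on the substudy ECG and concentration-QTc analyses: "as well as safety and limited efficacy based on the additional 45 evaluable subjects enrolled, will be performed separately from the primary analysis" of the 170 main-study subjects.
- Protocol Synopsis, Overview of Study Design, on subjects who joined the substudy early: "prior to Protocol Amendment 7 will continue with the assessments as required for the main study".

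**The concern.** The SAP limits the efficacy population to the main study and leaves the safety population open. SAP 3.1 and 4.12 count the substudy within Part 2, so a dosed substudy subject meets the Safety definition. Neither 4.5.5 nor 4.11.3 takes that subject out again. The rule as written therefore conflicts with the protocol synopsis.

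Three features make the substudy a different population for safety purposes.

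- **Disease and prior treatment.** Attachment 11 omits the main study's exclusions for del(5q) and for prior hypomethylating agents or lenalidomide (Protocol 4.2). Protocol 1.1.5.2.1 links cytopenia frequency and severity to prior chemotherapy and low marrow reserve.
- **Cardiac screening.** Attachment 11 is stricter here. It sets QTcF limits, excludes several rhythm and conduction abnormalities, and excludes New York Heart Association Class II upwards, where the main study excludes Classes 3 and 4.
- **Crossover.** After at least two cycles a substudy subject without evident benefit may be unblinded and, if on placebo, may start imetelstat. SAP 4.5.2 gives no rule for a subject who has received both. Protocol 3.2 and Figure 3 send main-study placebo subjects to follow-up, so this difficulty would reach the main tables only through the substudy.

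At stake is whether the safety tables describe the same randomised population as the efficacy tables with which they will be weighed.

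**Working it through.** **Inputs.** Part 1: 57 subjects. Main study of Part 2: about 170, as 115 imetelstat and 55 placebo (SAP 4.12). Substudy: about 45, as about 30 imetelstat and 15 placebo (Protocol Attachment 11).

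**Plan's own total.** 57 + 170 + 45 = 272, which agrees with the stated figure of about 270. The 45 are therefore additional to the 170.

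**Part 2 Safety set, limited to the main study.** At most 115 + 55 = 170.

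**Part 2 Safety set as written, upper case.** This assumes that every planned subject is dosed and falls inside the data cut.

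- Total: 170 + 45 = 215, an increase of 45/170 = 26%. Substudy share 45/215 = 20.9%.
- Imetelstat: 115 + 30 = 145. Substudy share 30/145 = 20.7%.
- Placebo: 55 + 15 = 70. Substudy share 15/70 = 21.4%.

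**Fewer substudy subjects in the cut.** With k dosed substudy subjects present, the share is k/(170 + k). The documents do not give k at the primary cut, so these values are assumptions:

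| k | Share of Part 2 Safety set |
|---|---|
| 0 | 0% |
| 15 | 15/185 = 8.1% |
| 30 | 30/200 = 15.0% |
| 45 | 45/215 = 20.9% |

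A smaller k is likely at the primary analysis. Attachment 11 holds back substudy enrolment until main enrolment is complete, except for subjects known to be ineligible for the main study. The synopsis also allows substudy data to arrive after the main primary analysis. In the other direction, 45 counts evaluable subjects and non-evaluable ones may be replaced, so the number dosed could end slightly above 45.

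**Crossover, limiting case.** If all 15 substudy placebo subjects later started imetelstat, imetelstat-exposed subjects would number 115 + 30 + 15 = 160, of whom 45/160 = 28% would come from the substudy.

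**Early substudy participants.** Subjects who joined before Amendment 7 follow main-study assessments (Synopsis; Protocol 3.1), yet they also fit the 4.5.5 definition, which has no date limit. Other parts of the SAP (3.2.3, 4.11.4 to 4.11.6) do add the Amendment 7 qualifier. The number of such subjects is not stated.

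**The case against.** The strongest reply is that separation was plainly intended. The SAP has its own substudy set, and its revision history records a change made to separate the substudy from the main study. The introduction to Protocol Section 11 confines that section to Part 1 and the main study, so the reference in 11.1 to all treated subjects sits under a main-study scope. Attachment 11 speaks of summarising cardiac events in two populations. SAP 4.5 also provides for a meeting on analysis sets, with decisions documented before unblinding.

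All of this stands as evidence of intent. A reader might infer from 4.5.2 that the sponsor plans to pool, and the documents do not support that. But intent does not change what 4.5.2 says, and a classification meeting applies definitions; it does not repair one that includes the wrong subjects.

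The reply is also right that the arms stay balanced in substudy share (20.7% against 21.4%), because the substudy too is randomised 2:1. Eligibility differs in both directions, looser on disease history and stricter on the heart, so the net effect cannot be signed.

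Three further inferences go too far:

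- **Early participants counted twice.** Their membership of two sets is overlap, which is common among analysis sets. Nothing in the documents adds the sets together.
- **A stated shift in a toxicity rate.** No document gives safety rates for the substudy population, so any such figure would be invented.
- **The same limit on the biomarker and PK/PD sets.** Biomarker assessments are not required in the substudy and the biomarker set needs a baseline sample, so little would change. Protocol 3.2 intends substudy and sparse PK data to feed one population model, which a restriction would obstruct.

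**Conclusion.** The definition is wrong as written and should be fixed. It conflicts with the protocol synopsis and does not match the main-study limit on the ITT set. On the planned numbers it could admit at most about 45 substudy subjects to a Part 2 Safety set of about 215 (21%), assuming all are dosed and in the cut; at the primary analysis the number is probably lower. The size and direction of any effect on safety rates are unknown. The primary endpoint, key secondary endpoints, type I error and power rest on the ITT set, which is correctly limited, and the safety analyses are descriptive. That makes this a definition to correct before Part 2 is unblinded, with no bearing on the efficacy conclusion.

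**What to change.** 1. SAP 4.5.2: for Part 2, define the Safety set as subjects randomised into the main study who received one or more doses of study drug. Leave Part 1 as it is.
2. State that substudy safety is reported on the 4.5.5 set.
3. SAP 4.5.5: limit the set to subjects enrolled in the substudy under Amendment 7 or later, so that earlier participants are counted only in the main study.
4. Label any display that combines the main study and the substudy as supplementary.

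The first change also keeps the unresolved substudy crossover out of the main safety tables. The cost is a few words in two SAP sections and the corresponding set flags, with no new data and no change to the efficacy analyses.

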4.5.3 Biomarker Analysis Sets

For both Part 1 and 2, the Biomarker analysis set includes all subjects who received at least one dose of study drug and had at least one biomarker sample at baseline collected.

4.5.4 Pharmacokinetics (PK)/ Pharmacodynamics (PD) Analysis Sets

For both Part 1 and 2, the PK analysis set includes all subjects who received at least one dose of study drug and had at least one post-dose quantifiable plasma sample. The PD analysis set includes all subjects who had at least one quantifiable post-dose determination on biomarker, efficacy or safety parameters as defined in the related Pharmacodynamics analysis plan.

4.5.5 Ventricular Repolarization Substudy Analysis Sets

The Ventricular Repolarization substudy analysis set includes all subjects who participated in Ventricular Repolarization substudy and received at least one dose of study drug.

4.6 Demographic and Other Baseline Characteristics

All demographic and baseline characteristic variables will be summarized for the All Treated analysis set for Part 1 and the ITT analysis set for Part 2.

The stratification factors used during randomization for Part 2 (prior RBC transfusion burden and IPSS risk group) will be tabulated. And values of prior RBC transfusion burden and IPSS risk group recorded on the electronic case report form (eCRF) will be summarized in transfusion history and disease characteristics as mentioned below. Any discrepancy between two data sources will be summarized as well.

Demographics and baseline characteristic data will be summarized, including sex, age (year), race, Eastern Cooperative Oncology Group (ECOG) performance status, weight (kg), and height (cm).

Hepatitis serology tests at baseline will be summarized by test type and results. Two panels of baseline clinical laboratory tests specified will be summarized: hematology and serum chemistry. Frequencies of National Cancer Institute (NCI) Common Terminology Criteria for Adverse Events (CTCAE) grade at baseline will be reported.

Disease characteristics to be summarized will include French-American-British (FAB) classification and World Health Organization (WHO) classification, IPSS risk category (low, intermediate-1), IPSS-R risk category (very low, low, intermediate, high, very high) [3], prior ESA treatment (Yes, No), serum EPO level (≤ 500 mU/mL, > 500 mU/ml), and time since initial diagnosis (month).

Transfusion history summaries will include total RBC transfusion units in the 16 weeks prior to study entry and prior RBC transfusion burden. Prior RBC transfusion burden is defined as the maximum number of RBC units transfused over an 8-week period during the 16 weeks prior to CID1 for subjects enrolled in Part 1 or the day of randomization for subjects enrolled in Part 2. Per revised IWG 2018 [4], the low transfusion burden (LTB) subject is who received 3 to 7 RBC units in the 16 weeks prior to study entry in at least 2 transfusion episodes. The high transfusion burden (HTB) subject is who received ≥ 8 RBC units in the 16 weeks prior to study entry in at least 2 transfusion episodes.

Medical history will be summarized including abnormality in physical examination. In addition, summaries of bone marrow (BM) findings at baseline will be provided.

4.7 Concomitant Medication

Medication start and stop dates will be compared to the date of first dose of study drug to allow medications to be classified as either Prestudy, Concomitant, or Subsequent.

Medications that start prior to the date of first dose of study drug will be classified as Prestudy. Medications will be classified as Concomitant if used between the date of first dose of study drug

and the last dose date + 30 days. A medication used after the last dose + 30 days is considered as Subsequent.

Medication will be coded using the latest version Anatomical Therapeutic Chemical (ATC) dictionary. Use of prestudy, concomitant or subsequent medications will be summarized by ATC class and drug generic term. Best response to last line of prior anticancer therapy will also be summarized. By-subject listings of concomitant medication details will be provided.

